- Quality of life/functional outcome comparisons using the KOOS Jr score, Oxford Knee Score (OKS), numerical rating scales (NRS) of gait/walking ability and sleep.
- Post-operative recovery comparisons using the Quality of Recovery 15 (QoR-15) survey and comparing average length of stay (LoS) for each study group

Questions to be answered:

- Is IORA of Diclofenac or systemic Diclofenac more effective in managing post-operative pain (as judged by VAS-P scores).
- 2. Will IORA of combined Diclofenac or systemic Diclofenac result in a more significant reduction in additional systemic opioid use for post-operative analgesia (as judged by MME).
- 3. Will IORA of Diclofenac or systemic Diclofenac provide better clinical improvement in knee health recovery and outcomes (as judged by KOOS Jr, OKS, NRS gait/walking ability and sleep, QoR-15, LoS).

Study Design

A prospective, double blinded RCT, with a single site cohort.

Patients and Methods

Patients who will be undergoing primary TKA for osteoarthritis will be eligible for this prospective study and randomised into two groups with 23 participants in each, one group receiving IORA Diclofenac (intervention group), and one group receiving IV Diclofenac (control group).

Power Calculation

There is a paucity of data evaluating the efficacy of IORA in pain management following TKA because it is a novel technique, although postoperative pain management is a thoroughly investigated area. Sample size was calculated based on previously published data investigating the efficacy of perioperative Celecoxib (a NSAID) on postoperative pain (VAS pain) after TKA [32]. This study showed statistically significant improvements in VAS pain scores for the intervention group (Celecoxib and PCA Morphine) at 48 hours and 72 hours after TKA, compared to the control group (PCA Morphine only). Mean VAS pain scores (in mm) in the intervention group were 21.3 ± 16.8 at 48 hours, and 17.8 ± 16.6 at 72 hours. Whereas VAS pain scores in the control group were 34.3 ± 15.0 at 48 hours, and 31.7 ± 20.1 at 72 hours.

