Multiple surgeons who regularly perform TKA will carry out this procedure on all patients included in the trial. Prior to all surgeries, each patient will undergo a general anaesthetic (GA) for their procedure, and no patients will have a neuraxial and/or peripheral nerve block. This will involve total IV anaesthesia with IV Propofol and IV fentanyl, as well as Ketamine and/or Clonidine in small amounts as adjuncts to the GA. The airway will be maintained via laryngeal mask airway. As part of usual TKA protocol 2g IV Cephazolin, 2g IV Tranexamic acid, and 16mg IV Dexamethasone will also be administered. The Patient will then be positioned appropriately for surgery and a single cuff tourniquet applied to the upper thigh of the marked limb. Following standard patient preparation

and draping of the appropriate limb, the limb is exsanguinated, and the tourniquet inflated to cease blood flow in the limb at 250-300 mmHg for the duration of the procedure (60-90 minutes). A proximal tibial IO cannula will then be inserted, and the study medication administered into bone immediately before skin incision [6, 7].

There will be two groups into which patients will be randomised; 23 patients will be randomised into each group:

- Group 1: IORA 75mg Diclofenac preoperatively (intervention group).
- Group 2: IV infusion 75 mg Diclofenac preoperatively (control group).

For the patients randomised to the IORA Diclofenac group, following tourniquet inflation a proximal tibial cannula will be inserted. The study medication will be administered via the cannula into bone immediately before skin incision. 75mg Diclofenac (75 mg/3 mL ampoules) will be made up to 10mL with normal saline 0.9% in a syringe to dilute the medication prior to administration. The medication will then be injected as a bolus by the blinded surgeon. Immediately after, 500 mg of Vancomycin in 110 mL normal saline 0.9% will be delivered intraosseously. These patients will also receive a preoperative IV infusion of 100 mL normal saline 0.9% over 2 minutes by the blinded anaesthetist. The infusion will finish at least 3 minutes prior to tourniquet inflation.

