The patients randomised into the second group will receive an IV infusion over 2 minutes of 75 mg Diclofenac (75 mg/3 mL ampoule) diluted to 100 mL with normal saline 0.9%, to finish at least 3 minutes prior to tourniquet inflation, by the blinded anaesthetist. Diclofenac (Voltaren™) 75 mg/3 mL solution has been approved by New Zealand Medsafe for intravenous infusion, but requires to be diluted. There are injectable Diclofenac formulations which can be administered as bolus, however these are not available in New Zealand. 10 mL of normal saline 0.9% will be given via IO after tourniquet inflation, followed by the same preparation of Vancomycin by the blinded surgeon.

An unblinded researcher (not the surgeon or anaesthetist) will prepare the medication as described above, according to the participant's group allocation. The preparation for IV infusion will be given to the blinded anaesthetist, and the preparation for IO injection will be given to the blinded surgeon.

All patients will also receive intraoperative local infiltration anaesthesia prior to skin closure in the form of 150 mL of 0.2% Ropivacaine with 0.3mcg of Adrenaline 1:1000 (0.3 mL). This is placed intra-articular and in the tissue surrounding the knee. Weight based dosage of ropivacaine will be used if patients are small.

Patients in all study groups will receive a standardised regimen of pain relief (unless certain medications are contraindicated) post-op as an inpatient and on discharge. Post-op analgesia includes IV Morphine 1-2 mg (in recovery only), Paracetamol 1 g PO QID, Celecoxib (dose will be prescribed according to weight/age), Tramadol modified release 100 mg PO BD, Gabapentin (dose will be prescribed according to weight/age), and Sevredol 10 mg PO Q1H PRN. The same preparation of Paracetamol, Celecoxib, Tramadol, and Gabapentin will be prescribed on discharge, but Sevredol will be reduced to 10 mg PO Q4H.

Informed Consent

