This will be achieved via a complete randomisation process using computerised sequence generation (random number generator) in a 1:1 ratio. Sealed, opaque envelopes which have been sequentially numbered will be used as the method of concealment. The envelopes will contain a randomised group allocation and instructions of medication preparation for administration. These will be prepared by an independent member of staff. The envelopes are to be sequentially numbered, as per the generated sequence, in advance for allocation to patients once they have consented to the trial. Once a patient has met the criteria for enrolment and has given informed consent, they will be allocated a randomisation envelope by the investigator or designee. Envelopes will be opened sequentially only after the participant's name has been written on the appropriate envelope. The investigator or designee will note the randomisation number in the patient's Case Report Form and this will be used as the patient's study ID number. Patient's will be blinded to their group allocation.

A patient information leaflet will be provided to the patient at their preoperative clinic appointment. Randomisation is to occur at the time of consent (which is usually the day prior to surgery) to allow for the appropriate orders to be made to ensure the study medication can be administered on time. The assigned envelope will be handed to a researcher on the day of the procedure, who will begin preparing the study medication for the appropriate study group.

Blinding

Patients, surgeons, and anaesthetists will be blinded to group allocation. Patients will be under general anaesthetic at the time of study medication administration, so will not be aware of which mode of study medication has been given. An unblinded researcher will prepare a 10 ml syringe with either normal saline 0.9% (control group), or 75mg Diclofenac made up to 10 mL with normal saline 0.9% (intervention group). The fluid will be passed onto the sterile field for administration by the treating surgeon.

An infusion of either 75mg Diclofenac made up to 100 mL with normal saline 0.9% (intervention group), or 100 mL normal saline 0.9% (control group) will be prepared by an unblinded researcher and handed over to the anaesthetist (blinded) for the preoperativeIV infusion.

Evaluations/Patient Outcome Measurements

Patient Demographics

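### The Blinding section reverses the two IV infusion labels: followed literally, the intervention group gets diclofenac by both routes and the control group gets none

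*Protocol*

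**What the plan says.** Patients and Methods defines the two arms by route: "one group receiving IORA Diclofenac (intervention group), and one group receiving IV Diclofenac (control group". The treatment description after the Exclusion Criteria repeats this with doses: "Group 1: IORA 75mg Diclofenac preoperatively (intervention group" and "Group 2: IV infusion 75 mg Diclofenac preoperatively (control group".

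The same description then gives each arm a dummy for the other route.

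- Intervention group, IV route: "These patients will also receive a preoperative IV infusion of 100 mL normal saline 0.9% over 2 minutes by the blinded anaesthetist".
- Control group, IV route: "The patients randomised into the second group will receive an IV infusion over 2 minutes of 75 mg Diclofenac", diluted to 100 mL.
- Control group, bone route: "10 mL of normal saline 0.9% will be given via IO after tourniquet inflation".

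The Blinding section restates what the unblinded researcher prepares. For the 10 mL bone syringe it says "either normal saline 0.9% (control group), or 75mg Diclofenac made up to 10 mL with normal saline 0.9% (intervention group", which agrees with the treatment description. For the infusion it says "75mg Diclofenac made up to 100 mL with normal saline 0.9% (intervention group), or 100 mL normal saline 0.9% (control group", which is the reverse.

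**The concern.** The protocol gives two incompatible instructions for the contents of the IV infusion. Under the treatment description, each patient receives one active product and one dummy. Under the Blinding section, intervention patients receive two active products and control patients receive two dummies.

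Two things are at stake. The first is the question the trial asks. The primary objective is to show that the intraosseous regional route is superior to systemic diclofenac, which requires the same drug and dose in both arms with only the route differing. If one arm had twice the planned dose and the other had none, the effects of drug, dose and route could not be separated. The second is exposure. Intervention patients would receive twice the dose defined for their group, of an NSAID whose systemic risks the protocol sets out in Appendix 2. Control patients would go without the analgesic that their group definition assigns to them.

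The mistake would also be hard to detect at administration. The surgeon and anaesthetist are blinded and each receives one prepared product, the patient is under general anaesthesia, and the protocol describes no second check of what has been prepared.

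**Working it through.** No sample-size or power figure is involved. The check is to set the contents side by side and add up the diclofenac in each arm.

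**Contents by group and route**

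| Group | Route | Treatment description | Blinding section | Agree? |
|---|---|---|---|---|
| Intervention | Bone, 10 mL syringe | 75 mg diclofenac | 75 mg diclofenac | Yes |
| Intervention | IV, 100 mL infusion | Saline | 75 mg diclofenac | **No** |
| Control | Bone, 10 mL syringe | Saline | Saline | Yes |
| Control | IV, 100 mL infusion | 75 mg diclofenac | Saline | **No** |

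**Diclofenac per patient = bone content + IV content**

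| Group | Treatment description | Blinding section read literally |
|---|---|---|
| Intervention | 75 + 0 = 75 mg | 75 + 75 = 150 mg |
| Control | 0 + 75 = 75 mg | 0 + 0 = 0 mg |
| Difference between groups | 0 mg | 150 mg |

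**Which text is wrong.** The treatment description agrees with the group definitions in Patients and Methods and with the stated objectives. The Blinding section agrees with them for the syringe but not for the infusion. Swapping the two group names in the infusion sentence gives 75 + 0 = 75 mg for intervention and 0 + 75 = 75 mg for control, and every section then agrees. The error therefore lies in that one sentence.

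**Number exposed.** With 23 patients per group, 2 × 23 = 46 would be affected if the Blinding section were used throughout. If preparers sometimes followed one text and sometimes the other, the share affected would be unknown and the arms would be mixed.

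**The case against.** The intended design is not in doubt. The title, the objectives, the group definitions and the full treatment description all agree, and one sentence stands against them. Read literally, that sentence leaves the arm named for IV diclofenac with no diclofenac, which marks it as a slip and not a rival design. The treatment description also tells the unblinded researcher to prepare the products as set out there. The working instruction on the day is the insert in the randomisation envelope, which is not shown, and nothing indicates that it carries the error. Finally, the researcher prepares both products and knows the allocation, so drawing up two active products or two dummies for one patient might well look wrong to that person.

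Most of this stands. It shows what was meant, and it means that the 150 mg versus 0 mg contrast is a worst case and not an expected outcome. It also limits the point about detection: the blinded staff could not notice, but the researcher might.

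It does not remove the need to correct the text. The faulty sentence is itself worded as a preparation step, and the protocol does not say which section prevails. It also sits next to the syringe sentence, with both products labelled by group, so it is a natural text to copy into an envelope insert. Because the protocol requires conduct according to the approved text, either way of preparing the infusion departs from one of its instructions.

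**Conclusion.** The contradiction is real and must be corrected before the protocol is used. The Blinding section's infusion sentence is wrong as written. If followed, it changes the comparison from 75 mg versus 75 mg to 150 mg versus 0 mg, for up to all 46 patients, and the trial could not answer its primary question about route.

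The harm is conditional. It depends on the envelope inserts or the preparer following the Blinding section and not the treatment description, and the protocol alone does not show which they follow. Nothing in it shows that anyone has been misdosed. The conclusion about which text is correct rests on the agreement of the title, objectives, group definitions and treatment description.

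**What to change.** 1. In the infusion sentence of the Blinding section, swap the two group names, so that the diclofenac infusion belongs to the control group and the saline infusion to the intervention group.
2. Preferably, state the contents once in a small table (group by route by contents), have the other sections refer to it, and copy it word for word into the envelope inserts:

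| Group | Bone, 10 mL syringe | IV, 100 mL infusion |
|---|---|---|
| 1. Intervention | 75 mg diclofenac in saline | Saline |
| 2. Control | Saline | 75 mg diclofenac in saline |

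3. Have a person independent of the blinded team check any envelope inserts already prepared against this allocation.
4. If any patient has been treated, verify from the preparation records what was given by each route, and document any departure as a protocol deviation.

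The cost is a one-sentence amendment, with the ethics approval that the protocol requires for any modification, and a check of the inserts. Sample size, procedures and analysis do not change.

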- NRS for gait/walking ability, sleep. To be recorded for 1 week post-op.
- Participant length of hospital stay, from date of admission to date of discharge.
- NRS for patient satisfaction, recorded at post-op weeks 2 and 6.
- KOOS, JR scores at post-op weeks 2 and 6.
- OKS at post-op week 6.

Indirect measure of pain will be gauged from the total MME dosing for each patient which will be an indicator of postoperative opioid use burden. Patients will be required to record in their pain diaries the amount, in milligrams, of additional opioid medication they are taking per day up to post-op day 7, which will then be converted into daily MME. Patients will also be required to record on a NRS how much pain has interfered with their walking ability and sleep over the previous 24 hours, up to post-op day 7 in their pain diaries.

[figure not shown]
An automated texting service will be used to remind patients to fill out their pain diary.

Length of stay from date of admission to date of discharge will be recorded for all participants on their pain diaries. Average length of stay will be calculated for each study group and compared.

Participants will be followed up in a 2 week post-op clinic where the pain diaries are to be collected. At this clinic, participants will be required to complete a KOOS Jr survey and NRS for patient satisfaction relating to their knee replacement. At the 6-week post-op mark patients will be seen in clinic again and will be required to complete a KOOS Jr survey, patient satisfaction NRS, and OKS. The means of these outcomes will be compared between the study groups at each particular time point.

Participants will be provided patient information leaflets detailing potential adverse effects of Diclofenac. If any adverse effects occur, participants are to report to nursing staff, who will inform the treating doctor/researcher. We predict side effects from a single preoperative dose of Diclofenac are unlikely to arise after discharge i.e., a few days post-op.

Study Timeline

Data Capture and Analysis

Data will be recorded on Case Report Forms (CRFs; includes patient pain diaries). An investigator will complete and sign forms once they are completed by patients. The data will then be entered onto a secure excel spreadsheet by a research assistant. The original paper CRFs are to be stored securely, and archiving to be undertaken in accordance with ICH/GCP guidelines.

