Definitions and Reporting of Adverse Events

Definitions

Adverse Events:

Any undesirable clinical occurrence in a subject, whether it is considered to be study
medication related or not, that includes a clinical sign, symptom, or condition; and/or an
observation of an unintended technical procedural error.

Expected:

An adverse event is expected when the specificity and severity of the event is consistent with
a complication that is not related to the study specific medications or procedural technique,
but may be related to the surgical procedure

Unexpected:

• An adverse event is unexpected when the specificity or severity of an adverse event is not consistent with the standard. It refers to an adverse event that has not been observed before

Adverse Study Medication Event:

• A clinical sign, symptom or condition that is causally related to the product, administration of the product, or performance of the product.

Serious Adverse Event:

- Any untoward medical occurrence that:
 - Results in death,
 - Is life threatening,
 - Requires inpatient hospitalisation or prolongation of hospitalisation,
 - Results in persistent or significant disability/incapacity,
 - May have caused a congenital anomaly/birth defect,
 - Requires intervention to prevent permanent impairment or damage,
 - Is a medically important event or reaction.

IRAD Study Study Study Protocol

Reporting of Events

Adverse Events:

Any adverse event that occurs at any point in time from the beginning of the surgical procedure until either the participant is terminated from the study, or 7 days post-completion, should be recorded as follows:

- All information on general medical, operative, and study medication related complications (adverse events) will be documented on Case Report Forms.
- Information should include date of occurrence, description, severity, relationship to study medication, treatment, and date of resolution.
- The investigator will determine if the event is related to the study medication.
- Any adverse event in a study patient must be monitored until it has resolved or been considered non-clinically significant by the investigator.

Expected Events:

Should be reported to the principal investigator as soon as possible, but not later than five working days after the investigator first learns of the event

Adverse Study Medication Events

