There have been isolated reports of fracture following intraosseous needle placement in the literature. This is thought to relate to the use of excessive force with manual needle placement, and to our knowledge has not been reported with the powered needle driver used in the current study.

4) Infection / osteomyelitis

A meta-analysis of 4359 intraosseous insertion attempts reported an incidence of infection of 0.6% [26]. It is anticipated that as the insertions in our study will take place in a fully sterile environment and antibiotic will be injected through the needle the incidence of infection is likely to be even lower.

The above complications will be outlined in the patient information sheet.

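### Adverse events are to be recorded until 7 days after completion, but the protocol states no enquiry about them, and no participant reporting route, specific to the period after discharge

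*Protocol*

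**What the plan says.** **Recording window.** Under Reporting of Events, adverse events are recorded from the start of surgery "until either the participant is terminated from the study, or 7 days post-completion, should be recorded as follows". Serious adverse events are recorded from consent, with the same end. The definition of an adverse event covers any undesirable clinical occurrence, whether or not it is related to the study medication.

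**Participant route.** Postoperative Outcome Measurements gives one instruction: "If any adverse effects occur, participants are to report to nursing staff, who will inform the treating doctor/researcher". The sentence before it concerns the drug: "Participants will be provided patient information leaflets detailing potential adverse effects of Diclofenac". So does the sentence after it: "We predict side effects from a single preoperative dose of Diclofenac are unlikely to arise after discharge i.e., a few days post-op".

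**Contacts after discharge.** The diary runs to day 7 and holds pain scores, opioid amounts, and walking and sleep ratings; length of stay is also entered on it. Of the week 2 clinic the protocol says: "At this clinic, participants will be required to complete a KOOS Jr survey and NRS for patient satisfaction relating to their knee replacement". The week 6 clinic adds the Oxford Knee Score. The Patient Evaluation Schedule has no adverse event row.

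**Harms named.** Appendix 1 lists compartment syndrome, cellulitis, osteomyelitis, fat embolism, inability to remove the needle, and fracture. On infection it says: "A meta-analysis of 4359 intraosseous insertion attempts reported an incidence of infection of 0.6" per cent. It expects a lower figure in this study and says the complications will be outlined in the patient information sheet.

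**The concern.** The window and the stated means of filling it do not match well. The window is wide in time and in scope: it runs to 7 days after completion and covers events of any cause. The stated route is passive, relies on the participant telling nursing staff, and stands beside a prediction about a single drug dose. That prediction says nothing about complications of the needle, which every participant receives.

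If participants are not asked in a uniform way after discharge, a low count of later events cannot be told apart from incomplete enquiry. This matters because fewer systemic side effects are part of the stated rationale for regional delivery, and because Data Capture and Analysis plans to tabulate adverse events and compare the groups by logistic regression. It also matters to the individual participant, whose later complication may not reach the trial team, particularly if it is treated elsewhere.

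**Working it through.** The plan gives no figure for this point, so there is none to reproduce. The check has three parts.

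**1. Length of the recording window.** Inputs: week 6 visit with a window of plus or minus 2 weeks (Visit Windows); end of recording at 7 days after completion (Reporting of Events). Completion is not defined; I assume it is the week 6 visit.

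- On-time visit: 6 × 7 + 7 = day 49.
- Earliest allowed visit (week 4): 4 × 7 + 7 = day 35.
- Latest allowed visit (week 8): 8 × 7 + 7 = day 63.

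On the same assumption, no contact is scheduled in the last 7 days of the window.

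**2. What each contact or process requires.**

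| Place in the protocol | What it requires | Does it state that participants are asked about harm? |
|---|---|---|
| Patient Evaluation Schedule | Baseline and outcome measures | No |
| Diary, to day 7 | Pain, opioids, walking, sleep, length of stay | No |
| Week 2 clinic | Diary collection, KOOS Jr, satisfaction | No |
| Week 6 clinic | KOOS Jr, satisfaction, Oxford Knee Score | No |
| Reporting of Events | Complications documented on case report forms and followed to resolution | No; says where and how an event is recorded |
| Patient Accounting; Data Quality Assurance | Regular monitoring of data; review of forms for completeness and patient risk | No; works on data already collected |
| Data Quality Assurance (research team) | Capture of complications not yet documented | No; assigns the duty without saying how |

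The last three rows are real safeguards that continue after discharge. None specifies a question to the participant.

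**3. Scale of the named harms.** Inputs: 23 participants per arm, so 46 in total; both arms receive an intraosseous injection (diclofenac or saline, then vancomycin), so all 46 are exposed. Appendix 1 cites 0.6% for infection and below 1% for intraosseous complications overall.

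- Expected infections: 46 × 0.006 = 0.28.
- Chance of at least one infection: 1 − (1 − 0.006)^46 = 0.242, or 24%.
- Chance of at least one complication, taking 1% as the upper bound: 1 − (1 − 0.01)^46 = 0.370, or 37%.

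These are chances that any such event occurs at the cited rates. They are not chances that an event occurs late or is missed. The documents give no onset times and no capture rates, so those cannot be computed.

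**The case against.** The strongest reply is that collection does not stop at discharge. Participants are seen at weeks 2 and 6, all complications go on case report forms, forms are reviewed for patient risk, and the research team must capture what has not been documented. Adverse events are recorded separately, which could explain why the schedule has no row for them. The information sheet, which is to outline the intraosseous complications, and the case report forms are not among the documents reviewed; either may hold a contact route or a prompt. This stands, and it limits the point to what the protocol itself fixes. It does not remove it: a contact number would yield spontaneous reports, and the clinic tasks as listed contain no enquiry.

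A reader might go further and infer that reporting ends at discharge, or that nobody will ask about harm. The text does not say so. It refers to nursing staff without naming a ward or an end date; the sentence about discharge makes an inpatient reading plausible but does not fix it. A clinician may well ask at either clinic. Nor can the days after discharge be counted as uncovered, since clinics and monitoring fall within them.

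Two further replies also stand. The diclofenac prediction is limited to the drug by its own wording, so it is not wrong within its scope; the difficulty is that it is the only statement about events after discharge in that section. And safety is not a listed objective: with 0.28 infections expected, even complete capture in 46 participants could not establish the safety of the needle for rare events.

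**Conclusion.** The point holds in a limited form. The protocol opens an adverse event window to about day 49 (day 35 to 63 across the allowed visit window), assuming completion is the week 6 visit. The participant route it states is passive and not specific to the time after discharge, and no scheduled contact is required to ask about harm. Later events, especially those treated elsewhere, may therefore be captured incompletely and unevenly between participants.

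The size of any under-capture cannot be estimated from the documents. The 24% and 37% show only that an intraosseous infection or complication somewhere in the trial is not remote at the cited rates, and the protocol expects infection to be less frequent here. That some of these complications present after discharge is a clinical inference, plausible for infection.

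A reader might also infer a biased comparison between arms. The documents do not support that for needle complications: both arms have the intraosseous injection and the same follow-up, so the main effect is a low overall safety count. This is an inexpensive improvement worth making, and it does not threaten the primary outcome.

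**What to change.** - Add an adverse events row to the Patient Evaluation Schedule, marked at 24 hours, discharge, week 2 and week 6.
- Add one line to the existing day 1 to 7 diary asking about any new symptom or medical visit.
- At the week 2 and week 6 clinics, ask every participant the same short list of questions, drawn from the harms named in Appendices 1 and 2 and including any care received elsewhere.
- State that the prediction about diclofenac effects after discharge does not limit adverse event collection in that period.

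**Cost:** protocol wording, one diary line and one form. The contacts already exist, so no extra visit is needed. The question list takes a few minutes per clinic, and prompted questions will record more minor events.
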